I. Administrative information:

Title:

Accuracy of linear measurements of ultra-low dose Cone Beam Computed Tomography and Digital Panoramic Radiography Performed on mandibular anaesthetic landmarks Versus Real mandibular measurements (Diagnostic Accuracy Study)

II. Introduction:

Background:

One of the important mandibular anatomical landmarks is the inferior alveolar Nerve which can be damaged during surgical procedures such as third molar extraction, management of trauma and surgical removal of tumors. Therefore the dentist must be able to localize it prior to any dental procedure (Patil et al 2015).

The mandibular foramen represents the entrance of the inferior alveolar nerve, which passes through the mandibular canal throughout the body of the mandible till it reaches the mental foramen where it divides into mental nerve and incisive nerve (Salinas et al 2016).

In the past, the anterior region of the mandible was regarded as a safe area for implant surgery due to the absence of neurovascular structures. However, recent studies have shown haemorrhage and hematoma formation in the floor of the mouth due to injury to the vessels of the mandibular lingual foramen (Rosano et al 2009).

Panoramic radiography is simple, inexpensive, and widely used, in addition to offering low radiation exposure to the patient. Kaffe et al 1994 found panoramic radiographs to be beneficial in locating mandibular foramen. In another study performed by Kositbowornchai et al 2007 it was found that there is a high accuracy between the distances measured on panoramic radiographs and real measurements on dry mandibles (Kaffe et al 1994) and (Kositbowornchai et al 2007).

Ultra-Low Dose CBCT technology is a recommended option for clinicians due to the decrease in radiation exposure to patients. Patients must not be exposed to a higher dosage than needed to acquire images of sufficient diagnostic quality (Kusnoto et al 2015)

Review of literature:

Resources: PubMed, Science direct.

In a study performed on dry mandibles the comparison of linear measurements made with digital caliper and CBCT showed no significant differences for 95% of the distances measured. The 5% discrepancy is considered acceptable (Kamburoglu et al 2011) and (Sanjana et al 2017).

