A study was performed to evaluate the accuracy of panoramic radiographs in the localization of mandibular foramen on dry mandibles, where the position of mandibular foramen in relation to the ramus width and height was noticed. The results showed that there were statistically significant differences between distances measured on dry mandibles and radiographs except for the upper anterior ramus height (**Kositbowornchai et al 2007**) and (**Patil et al 2015**).

Another study was conducted on dry mandibles for the localization of the mental foramen. Measuring the distances from the crest of the ridge to the center of the mental foramen and from the inferior border of the mandible to the center of the mental foramen in addition to the location of the mental foramen relative to its' alignment with mandibular teeth. For mental foramen measurement from crest of the ridge till its' center did not show a significant difference for laterality, while the distance from the inferior border of the mandible till the center of the mental foramen the results showed a significant difference. Studies have shown that the most common location of the mental foramen is aligned with the second premolar, followed by between the first and the second mandibular premolar (**Lopes et al 2010**).

A study was performed for the localization of the lingual foramen using CBCT. Linear measurements were made including their diameter, the distance between the lingual foramen and the crest of the ridge and the distance from the inferior border of the mandible to the lingual foramen. Lingual foramina were classified according to their location into midline type, Para median type or posterior type. (**He et al 2016**).

CBCT and panoramic radiographs have been used to detect and measure lingual foramina. It has been proposed that CBCT provides highly accurate data of the mandibular anatomy (**Ludlow et al 2007**) and (**Stratemann et al 2008**).

III. Methods:

A. The pre-analytical phase: Mandibular anaesthetic landmarks will be identified on each dry mandible and will be marked using gutta percha.

B. The analytical phase. The ten human dry mandibles will be submitted for:

1-Digital Panoramic Radiography.

Panoramic radiographs will be obtained using the SOREDEX CRANEX™ 3Dx unit. The exposure parameters will be 8Ma, 63kVp and 16.4 sec exposure time.

2-Cone Beam Computed Tomography (CBCT).

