SOREDEX CRANEX™ 3Dx unit will be used in this study. Images will be acquired at a single rotation. SOREDEX® MiniDose parameters will be used. The exposure parameters will be 3.2 Ma, 90kVp and 2.3 sec exposure time to take the advantage of 3D data in dose sensitive cases like children, or reduce the radiation dose for the patient.

The real linear measurements will be measured in millimeter on dry mandibles using digital caliper and will be compared with measurements obtained from both techniques.

C. The post analytical phase. Images will be evaluated by two experienced radiologists of ten years of experience. Each one will evaluate the images separately twice with a period of two weeks in-between the two reading sessions. The researcher will measure out the real linear measurements on the dry mandibles using digital caliper.

D) Statistical analysis

Sample size calculation and how it was determined

Sample size calculation was done using R statistical package, version 3.3.1 (21-06-2016). Copyright (C) 2016. The R Foundation for Statistical Computing.

One-way analysis of variance power calculation for more than two groups was used to detect the proper sample size. Means and standard deviations were determined according to Patil et. al (2015) based on the difference in distances measured on dry mandibles between different radiographic techniques.

The results showed that, at a power of 80% and a two-sided significance level of 5%; a total sample size of 10 dry mandibles will be adequate to reject the null hypothesis that the group means are equal; i.e there's no difference between radiographic techniques.

Sample Size Calculation statistical output

Name of the test: One-way analysis of variance (ANOVA) power calculation for more than two groups.

Source use for calculation:** Patil et. al, 2015

Output:

```
> m1=15.27
> sd1=1.57
> m2=16.93
> sd2=1.54
> n1=n2=25
> k=2
> within.var=(sd1^2+sd2^2)/2
> m=((n1*m1)+(n2*m2))/(n1+n2)
> between.var=(((m-m1)^2)+((m-m2)^2))/(k-1)
> power.anova.test(groups = 3, between.var = between.var, within.var =
within.var, power=0.80, sig.level=0.05)
```

Balanced one-way analysis of variance power calculation

groups = 3

n = 9.52841

between.var = 1.3778

within.var = 2.41825

sig.level = 0.05

power = 0.8

NOTE: n is number in each group

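### The three-group null used for sizing is not the same as no difference between the two radiographic techniques, and no direct comparison of CBCT error with panoramic error is described

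*Combined protocol and SAP*

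**What the plan says.** The analytical phase lists two imaging methods, "1-Digital Panoramic Radiography" and "2-Cone Beam Computed Tomography (CBCT", and sends all ten mandibles to them. The same Methods section adds caliper readings: "The real linear measurements will be measured in millimeter on dry mandibles using digital caliper and will be compared with measurements obtained from both techniques". The title gives the same orientation: "Performed on mandibular anaesthetic landmarks Versus Real mandibular measurements (Diagnostic Accuracy Study".

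Section D then states how the study was sized: "One-way analysis of variance power calculation for more than two groups was used to detect the proper sample size". The call is "power.anova.test(groups = 3, between.var = between.var, within.var" and so on, at 80% power and 5% significance, giving n = 9.52841 per group, taken as 10 mandibles. The null to be rejected is that "the group means are equal; i.e there's no difference between radiographic techniques".

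The three groups are not named. No hypothesis test is named for the final analysis, and no comparison of one technique's error with the other's is described.

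**The concern.** The explanatory clause in the null treats two hypotheses as one. Equality of three means, one of them presumably the reference, says that both techniques agree on average with the caliper. No difference between techniques says that CBCT and panoramic perform alike, whether or not either agrees with the caliper. The first can be false while the second is true: both techniques may be off by the same amount. Equal means can also hide unequal accuracy, when one technique simply scatters more widely around the true length.

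This is the only null in the plan, and the 80% power is attached to it. A reader could therefore take a significant three-group result as evidence that the techniques differ, or a non-significant one as evidence that they are alike. Separate tests of each technique against the caliper would not settle it either: one significant and one non-significant result is not a test of the difference between them.

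**Working it through.** **Inputs from section D.** Means 15.27 and 16.93 (difference 1.66); SDs 1.57 and 1.54; within-group variance (1.57² + 1.54²)/2 = 2.41825; between-group variance 1.3778; three groups; alpha 0.05.

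**1. Reproduce the plan's figure.** For a balanced one-way ANOVA with g groups, df = g − 1 and g(n − 1), and the noncentrality is λ = (g − 1) × n × between-variance / within-variance. With g = 3 and n = 9.52841, λ = 2 × 9.52841 × 1.3778 / 2.41825 = 10.86 and power is 0.800. At n = 10, λ = 11.40 and power is 82.2%. The arithmetic reproduces.

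**2. Count the groups.** There are two imaging methods and one caliper set. No other candidate for a third group is described, so the caliper is inferred.

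**3. Both techniques wrong by the same amount.** Put the caliper at 0 and both techniques at +1.66 mm.
- Grand mean = 3.32/3 = 1.1067.
- Sum of squared deviations = 1.1067² + 2 × 0.5533² = 1.837.
- λ = 10 × 1.837 / 2.41825 = 7.60; critical F(2, 27) = 3.354.
- Rejection probability = 0.641.

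The techniques do not differ, yet the null as worded would be rejected in 64% of trials. With both at +2.03 mm, which gives exactly the plan's between-group variance of 1.3778, it is 82.2%. So the stated power can be reached with no difference at all between the techniques.

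**4. What the sizing gives for a two-technique comparison.** An unpaired comparison of two groups differing by 1.66 with variance 2.41825 needs 14.8, so 15, per group for 80% power. At 10 per group it has 61.7%. A paired comparison depends on a correlation that the documents do not give.

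**5. Random and systematic error, by simulation.** Ten mandibles measured by all three methods; true-length variance 2.41825 (SD 1.555 mm). Error sizes are assumptions, since the documents give none. With zero bias the mean absolute error is SD × √(2/π), so SDs of 0.3 and 1.5 mm give 0.24 and 1.20 mm. Percentages are rejection rates, rounded.

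| Bias, CBCT / panoramic (mm) | Error SD, CBCT / panoramic (mm) | One-way ANOVA | Repeated-measures ANOVA | Paired absolute-error t test |
|---|---|---|---|---|
| 0 / 0 | 0.3 / 1.5 | about 0.3% | about 9% | about 92% |
| 0 / 0 | 0.5 / 1.0 | about 0% | about 7% | about 37% |
| 0.2 / 1.0 | 0.5 / 0.5 | about 4% | over 99% | about 80% |
| 0.332 / 1.66 | 0.5 / 0.5 | about 47% | about 100% | over 99% |
| 1.66 / 1.66 | 0.5 / 0.5 | about 62% | about 100% | about 5% |

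The last row repeats step 3 with matched data. Only the paired contrast holds its 5% level when the techniques err equally.

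**The case against.** The strongest reply is that the ANOVA appears only as a sizing device. That is right: a reader might infer that the three-group F test is the planned analysis, but the documents do not say so. The supportable statement is that no described test addresses the stated null. The rejection rates above apply only if the sizing test is also used for the analysis.

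Second, the caliper as third group is an inference. It is the only candidate described, but the plan does not label the groups. Whatever the third group is, three groups and two techniques do not fit the explanatory clause.

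Third, the title and the Methods set each technique against real measurements. Under that aim, rejecting when both read 1.66 mm high correctly detects inaccuracy. It becomes an error only if the result is read through the explanatory clause. The plan makes no superiority or equivalence claim between techniques. But its only null is worded as a comparison of techniques, so the clause needs correcting even if no such comparison is wanted.

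Fourth, a reader might infer that the three-group test will generally miss a fivefold difference in error. The documents do not support this. The miss shown needs zero bias and assumed error SDs. When the fivefold difference is in bias (0.2 v 1.0 mm), repeated-measures ANOVA detects it better than the paired absolute-error test; one-way ANOVA is weak there mainly because it ignores the pairing. Under independence, at 0.332 v 1.66 mm, a direct unpaired test has less power than the three-group F test (44% v 56%).

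Finally, mean absolute error is one accuracy measure among several and hides the direction of error. That stands, so it should be reported beside signed bias, not instead of it.

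**Conclusion.** The point holds as a mismatch between null, group count and power claim. If the third group is the caliper, the three-group null concerns agreement of both techniques with the reference, the 80% does not cover a comparison of the techniques, and the plan describes no such comparison.

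The false-positive direction is the firmer one. The 64% uses the plan's own difference, variance and n, and assumes only that the caliper is a group and that the F test is used for analysis. The missed-difference direction (about 0.3% and 9% against about 92%) is an illustration for purely random error and does not carry over to differences in bias. The plan should be corrected before analysis; nothing here questions the arithmetic of the stated n for the inputs entered.

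**What to change.** 1. In section D, delete the clause that explains the null as no difference between techniques. Alternatively, label the three groups, state that the null concerns agreement of both techniques with the caliper, and state that the 80% does not cover a comparison of the techniques.
2. Add that comparison. For each distance and mandible, take |CBCT − caliper| minus |panoramic − caliper|. Report the mean over the ten mandibles with a 95% CI from a paired t analysis, and a signed-rank test as sensitivity analysis. State beforehand how the four readings per image (two radiologists, two sessions) are combined.
3. Report it beside each technique's signed bias and limits of agreement against the caliper, so that the direction of error stays visible.
4. State that a claim that one technique is more accurate will not rest on the three-group test or on separate tests against the caliper.

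The cost is a wording change and one more analysis of data already planned, with no new specimens or exposures. The downside is that the contrast has no power behind it that the documents can support, so it should be reported with its interval and without a power claim.

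### The 80% power claimed for 10 mandibles is not supported: a variance of two means is entered as the variance of three, and no third mean is given

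*Combined protocol and SAP*

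**What the plan says.** Under III. Methods, D) Statistical analysis, the plan states that "One-way analysis of variance power calculation for more than two groups was used to detect the proper sample size". The means and standard deviations come from one published study and are described as "based on the difference in distances measured on dry mandibles between different radiographic techniques". The conclusion drawn is that "at a power of 80% and a two-sided significance level of 5%; a total sample size of 10 dry mandibles will be adequate".

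The R output in the same section shows how this was reached. Two means are entered (15.27 and 16.93, with SDs 1.57 and 1.54 and 25 per group), k is set to 2, and the between-group variance is computed as "between.var=(((m-m1)^2)+((m-m2)^2))/(k-1". The next call is "power.anova.test(groups = 3, between.var = between.var, within.var", with power 0.80 and significance level 0.05. It returns n = 9.52841 per group.

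On design, section B (The analytical phase) says "The ten human dry mandibles will be submitted for" panoramic radiography and CBCT. It adds that the real distances are measured on the dry mandibles "using digital caliper and will be compared with measurements obtained from both techniques". Each mandible therefore yields a measurement by all three methods.

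**The concern.** The between-group variance describes two means, but the power function is told that it describes three. The function cannot detect this, because it receives only the variance. No third mean is given anywhere in the document, and section D does not say which methods the two entered means represent.

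The power model also treats the three sets of measurements as independent groups, although they come from the same ten mandibles.

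This output is the only justification given for 10 mandibles. If it fails, the 80% has no basis in the plan. That matters for interpretation: a non-significant difference between an imaging method and the caliper could be read as evidence of accuracy on the strength of a power figure that was never established.

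**Working it through.** **Inputs (all from the R output in section D).** Means 15.27 and 16.93; SDs 1.57 and 1.54; 25 per source group; k = 2; groups = 3; alpha 0.05; power 0.80.

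**1. Reproducing the plan's figure.**
- Within-group variance: (1.57² + 1.54²)/2 = (2.4649 + 2.3716)/2 = 2.41825.
- Overall mean: (15.27 + 16.93)/2 = 16.10, so each mean deviates by 0.83.
- Between-group variance: (0.83² + 0.83²)/(2 − 1) = 1.3778.
- Power comes from the noncentral F distribution with df (g − 1) and g(n − 1), and noncentrality λ = (g − 1) × n × between/within.
- With g = 3 and between = 1.3778, 80% power requires n = 9.528, matching the printed value. At n = 10, λ = 2 × 10 × 1.3778/2.41825 = 11.40 and power is 82.2%.

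**2. Where the input fails.** The factor (g − 1) turns a variance of g means back into a sum of squared deviations. With g = 3 that is 2 × 1.3778 = 2.7556. The two stated means supply 0.83² + 0.83² = 1.3778, which is half.

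**3. What third mean would justify the entry.** For means 15.27, 16.93 and x, the sum of squared deviations is 1.3778 + (2/3)(x − 16.10)².
- For a variance of 1.3778 (sum 2.7556): (x − 16.10)² = 1.3778 × 3/2 = 2.0667, so x is about 14.66 or 17.54.
- For 80% power at exactly n = 10: x is about 14.74 or 17.46, which is 0.53 mm outside the range of the two stated means.

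**4. The plan's own test with consistent inputs (independent groups, within-group variance 2.41825).** The third mean is an assumption in the three-group rows.

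| Inputs | Between variance | λ at n = 10 | Power at n = 10 | n per group for 80% |
|---|---|---|---|---|
| As entered, g = 3 | 1.3778 | 11.40 | 82.2% | 9.53, so 10 |
| Third mean equal to either stated mean, g = 3 | 1.8371/2 = 0.9185 | 7.60 | 64.1% | 13.73, so 14 |
| Third mean midway (16.10), g = 3 | 1.3778/2 = 0.6889 | 5.70 | 51.2% | 17.95, so 18 |
| Two stated means only, g = 2 | 1.3778 | 5.70 | 61.7% | 14.80, so 15 |

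The midway case is the mathematical minimum for three groups. Setting groups to 2, to match k, does not restore 80% either.

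**5. The design as planned (repeated measures, 10 mandibles).** Assume compound symmetry with correlation ρ between methods within a mandible, and take 2.41825 as the total variance for each method. Then λ = n × 2 × between/(within × (1 − ρ)), with df 2 and 18.

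| ρ (assumed) | Third mean equal to a stated mean | Third mean midway |
|---|---|---|
| 0.2 | 72% | 59% |
| 0.4 | 84% | 72% |
| 0.6 | 96% | 88% |
| ρ needed for 80% | 0.34 | 0.50 |

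**The case against.** The strongest reply is that the two faults pull in opposite directions. The doubled sum of squares inflates power, while ignoring the repeated measurement of the same mandibles can understate it. Ten mandibles may therefore be enough, and the size of any net shortfall is unknown. This stands, and it limits the conclusion. It does not validate the printed 80%, because the plan neither states a correlation nor makes a repeated-measures calculation.

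A second reply is that nothing forces the third mean to lie between 15.27 and 16.93. A mean 0.27 mm outside the range gives about 72% at 10 per group, and one 0.53 mm outside gives 80%. That is also true, so the 51% to 64% range is conditional. But the code shows that 1.3778 was computed from two means, and no value outside the range is stated.

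A third reply is that the midway case is only a floor. The literature review reports that "the comparison of linear measurements made with digital caliper and CBCT showed no significant differences for 95% of the distances measured", which would place the CBCT and caliper means close together and favour the 64% case. That holds only if one of the two entered means is the caliper's. The literature review cites the same source study for a comparison of dry-mandible and radiographic distances, which suggests that it is. Section D, however, describes the inputs as differences between radiographic techniques. The question is not settled.

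**Conclusion.** The concern holds. The statement that 10 mandibles give 80% power is unsupported as written, because the calculation uses twice the sum of squared deviations that its two means provide and states no third mean.

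Under the plan's independent-groups test, and assuming a third mean at or between the two stated ones, power at 10 per group is 51% to 64% rather than the 82% implied by the call. These figures show how far the calculation is off on its own terms; they do not estimate the power of the study. With the same mandibles measured by every method, 10 could reach 80% if the within-mandible correlation is at least about 0.34 (third mean equal to a stated mean) to 0.50 (midway), under compound symmetry. The document gives no correlation, so whether 10 is enough remains open. The correction is needed because this output is the sole stated basis for the sample size.

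**What to change.** Replace the one-way calculation with a repeated-measures one that matches the design. State three assumed means and the method each represents (panoramic, CBCT, caliper), compute the between-method variance from all three, and give the assumed within-mandible correlation with its source. Show power at 10 mandibles over a plausible range of correlations.

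If the one-way calculation is kept, enter the variance of three explicit means and restate the power. With a third mean at or between the two stated ones, that is about 51% to 64% at 10 per group. The text should then say that this figure ignores the repeated measurement of each mandible.

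The cost is one rewritten paragraph and one revised R call. Correcting the statement does not itself require more mandibles. Keeping both 80% power and 10 mandibles does depend on justifying a sufficient correlation, or on a third mean far enough outside the stated range. The downside is a power statement that may be less favourable, or that rests openly on an assumed correlation.
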